8. INFORMED CONSENT, DATA PROTECTION, TRIAL RECORDS

The trial will be carried out in compliance with the protocol, the ethical principles laid down in the Declaration of Helsinki, in accordance with the ICH Harmonized Tripartite Guideline for GCP, relevant BI SOPs, and relevant regulations.

Standard medical care (prophylactic, diagnostic and therapeutic procedures) remains in the responsibility of the treating physician of the patient.

The Investigator will inform the Sponsor immediately of any urgent safety measures taken to protect the trial subjects against any immediate hazard, and also of any serious breaches of the protocol or of ICH GCP.

The rights of the Investigator and of the Sponsor with regard to publication of the results of this trial are described in the Investigator contract. As a rule, no trial results should be published prior to finalization of the Clinical Trial Report.

8.1 TRIAL APPROVAL, PATIENT INFORMATION, AND INFORMED CONSENT

This trial will be initiated only after all required legal documentation has been reviewed and approved by the respective IRB/ IEC and CA according to national and international regulations. The same applies for the implementation of changes introduced by amendments.

Prior to patient participation in the trial, written informed consent must be obtained from each patient (or the patient's legally accepted representative) according to ICH GCP and to the regulatory and legal requirements of the participating country. Each signature must be personally dated by each signatory and the informed consent and any additional patient-information form retained by the Investigator as part of the trial records. A signed copy of the informed consent and any additional patient information must be given to each patient or the patient's legally accepted representative."

Re-consenting may become necessary when new relevant information becomes available and should be conducted according to the Sponsor's instructions.

8.2 DATA QUALITY ASSURANCE

A quality assurance audit/inspection of this trial may be conducted by the Sponsor, Sponsor's designees, or by IRB/ IEC or by regulatory authorities. The quality assurance auditor will have access to all medical records, the Investigator's trial-related files and correspondence, and the informed consent documentation of this clinical trial.

c03317678-02 Trial Protocol Page 56 of 69

Proprietary confidential information © 2016 Boehringer Ingelheim International GmbH or one or more of its affiliated companies

8.3 RECORDS

eCRFs for individual patients will be provided by the Sponsor. See Section 4.1.5.2 for rules about emergency code breaks. For drug accountability, refer to Section 4.1.8.

8.3.1 Source documents

Source documents provide evidence for the existence of the patient and substantiate the integrity of the data collected. Source documents are filed at the Investigator's site.

Data reported on the CRF must be consistent with the source data or the discrepancies must be explained. The Investigator may need to request previous medical records or transfer records, depending on the trial; current medical records must also be available.

For eCRF all data need to be derived from source documents.

8.3.2 Direct access to source data and documents

The Investigator/ institution will permit trial-related monitoring, audits, IRB/ IEC review and regulatory inspection, providing direct access to all related source data / documents. eCRF and all source documents, including progress notes and copies of laboratory and medical test results must be available at all times for review by the Sponsor's clinical trial monitor, auditor and inspection by health authorities (e.g. FDA). The CRA/ on site monitor and auditor may review all eCRFs, and written informed consents. The accuracy of the data will be verified by reviewing the documents described in Section 8.3.1.

8.3.3 Storage period of records

Trial sites:

The trial site(s) must retain the source and essential documents (including ISF) according to the national or local requirements (whatever is longer) valid at the time of the end of the trial.

Sponsor:

The sponsor must retain the essential documents according to the sponsor's SOPs.

8.4 LISTEDNESS AND EXPEDITED REPORTING OF ADVERSE EVENTS

8.4.1 Listedness

To fulfil the regulatory requirements for expedited safety reporting, the Sponsor evaluates whether a particular adverse event is "listed", i.e. is a known side effect of the drug or not. Therefore, a unique reference document for the evaluation of listedness needs to be provided. For capsaicin/diclofenac gel, and active comparators containing the individual components this is the current version of the Investigator's Brochure [c03404356].

For paracetamol the reference document is the SmPC of Panadol Original Tablets[®].

Trial Protocol

c03317678-02 Page 57 of 69

Proprietary confidential information © 2016 Boehringer Ingelheim International GmbH or one or more of its affiliated companies

The current versions of these reference documents are provided in the ISF. No AE are classified as listed for matching placebo, trial design, or invasive procedures.

8.4.2 Expedited reporting to health authorities and IEC / IRB

Expedited reporting of serious adverse events, e.g. suspected unexpected serious adverse reactions (SUSAR) to health authorities and IRBs/IECs, will be done according to local regulatory requirements.

8.5 STATEMENT OF CONFIDENTIALITY

Individual patient medical information obtained as a result of this trial is considered confidential and disclosure to third parties is prohibited with the exceptions noted below. Patient confidentiality will be ensured by using patient identification code numbers.

Treatment data may be given to the patient's personal physician or to other appropriate medical personnel responsible for the patient's welfare. Data generated as a result of the trial need to be available for inspection on request by the participating physicians, the Sponsor's representatives, by the IRBs/ IECs and the regulatory authorities.

8.6 **END OF TRIAL**

The end of the trial is defined as last patient last follow-up visit (Visit 7T).

The IEC/CA in each participating EU member state needs to be notified about the end of the trial or early termination of the trial.

c03317678-02 Trial Protocol Page 58 of 69

Proprietary confidential information © 2016 Boehringer Ingelheim International GmbH or one or more of its affiliated companies

10. APPENDICES

Not applicable

21 Jun 2016

Page 61 of 69

c03317678-02 Trial Protocol Page 62 of 69

Proprietary confidential information © 2016 Boehringer Ingelheim International GmbH or one or more of its affiliated companies

11. DESCRIPTION OF GLOBAL AMENDMENT(S)

Number of global amendment	1
Date of CTP revision	21-Jun-2016
	2015-000404-25
EudraCT number	1358.1
BI Trial number	
BI Investigational Product(s)	Diclofenac + Capsaicin
Title of protocol	A randomized, controlled multi-centre parallel group study to assess the efficacy and safety of multiple doses of a topically applied combination containing diclofenac 2% + capsaicin 0.075% (2 g formulation per application; 2-times daily for 5 days) compared to placebo, as well as to diclofenac 2% and capsaicin 0.075% in patients with acute back or neck pain
To be implemented only after	
approval of the IRB / IEC /	
Competent Authorities	
To be implemented immediately	
in order to eliminate hazard –	
IRB / IEC / Competent	
Authority to be notified of	
change with request for	
approval	
Can be implemented without	
IRB / IEC / Competent	
Authority approval as changes	
involve logistical or	
administrative aspects only	
	mu.
Section to be changed	Title page
Description of change	Phone: Fax: Has been changed to:

c03317678-02 Trial Protocol Page 63 of 69

	Phone: Fax:
Dationals for shange	Change of responsibility
Rationale for change	Change of responsibility
Section to be changed	CLINICAL TRIAL PROTOCOL SYNOPSIS – Main criteria for inclusion
Description of change	Sensitivity to algometric pressure on the painful trigger point $\leq 2.5 \text{ N/cm}^2$
	Has been changed to:
	Sensitivity to algometric pressure on the painful trigger point ≤ 25 N/cm ²
Rationale for change	An upper limit of 2.5 N/cm² has turned out to be too low and would only allow the inclusion of patients with extremely high algometric pressure. This upper limit had been taken from Pabst et al. (2013), Phytother. Res. 27: 811–817. However, personal communication was received from (co-author of the publication and coordinating investigator of this trial) that actually and upper limit of 2.5 kp/cm² had been applied in the published study. 2.5 kp/cm² correspond to 24.5 N/cm².
Section to be changed	Flowchart
Description of change	Approximate day time of Visit 7T which was
Description of change	formerly given as "E" (evening) was removed.
Rationale for change	Visit 7T does not need to be performed at a specific day time
Section to be changed	Flowchart
Description of change	Hand-out of patient diary; Instructions on use: X at visit 1
	Has been changed to:
	Return of patient diary: X at visit1, visit 2, visit 3, visit 4, visit 5
Rationale for change	The patients get a new diary at each visit 1-5 and are supposed to return that diary at the very next visit
Section to be changed	Flowchart

c03317678-02 Trial Protocol Page 64 of 69

Description of change	Return of patient diary: X at visit 6
- confront or consign	First tanks
	Has been changed to:
	Return of patient diary: X at visit 2, visit 3, visit 4, visit 5 and visit 6
Rationale for change	The patients get a new diary at each visit 1-5 and are supposed to return that diary at the very next visit
Section to be changed	Flowchart
Description of change	Completion of patient participation (*)
	Has been changed to:
	Completion of patient participation
Rationale for change	Correction of typo
Section to be changed	3.3.2 Inclusion criteria
Description of change	4. Sensitivity to algometric pressure on the painful trigger point ≤ 2.5 N/cm² (see Section 5.2.2).
	Has been changed to:
	4. Sensitivity to algometric pressure on the painful trigger point ≤ 25 N/cm² (see Section 5.2.2).
Rationale for change	An upper limit of 2.5 N/cm² has turned out to be too low and would only allow the inclusion of patients with extremely high algometric pressure. This upper limit had been taken from Pabst et al. (2013), Phytother. Res. 27: 811–817. However, personal communication was received from (co-author of the dinating investigator of this trial) that actually and upper limit of 2.5 kp/cm² had been applied in the published study. 2.5 kp/cm² correspond to 24.5 N/cm².
Section to be changed	3.3.4.1 Removal of individual patients
Description of change	Patients who discontinue or withdraw from the study after randomisation will be considered as "early discontinuations" and the reason for this premature discontinuation must be recorded in

BI Trial No.: 1358.1

c03317678-02 Trial Protocol Page 65 of 69

	the eCRF. The Investigator must inform the
	sponsor within 24 hours via IRT (see Section
	4.1) about any discontinuation of a subject.
	Has been changed to:
	Patients who discontinue or withdraw from the
	study after randomisation will be considered as
	"early discontinuations" and the reason for this
	premature discontinuation must be recorded in
	the eCRF. The Investigator must inform the
	sponsor within 24 hours (see Section 4.1) about
	any premature discontinuation of a subject.
Rationale for change	The IRT system does not require to register the
	termination of a patient's trial participation
	T11 411 1 411 2 411 411 2 411
Section to be changed	Table 4.1.1: 1, table 4.1.1: 2, table 4.1.1: 3, table
	4.1.1: 4
Description of change	Semi solid formulation
	Has been changed to:
	This over changes to.
	Gel
Rationale for change	Correction
Section to be changed	

c03317678-02 Trial Protocol Page 66 of 69

 Proprietary confide	ntial information ©	2016 Boehringe	er Ingelheim Inte	rnational GmbH	or one or more	of its affiliated	companies

Section to be changed	Figure 5.2.1:5
Description of change	A downward showing arrow was added to the
	image
Rationale for change	Added for clarification
Section to be changed	5.3.3 Physical examination
Description of change	A physical examinations will be performed by
	the Investigator or designated site-personnel at
	the time point indicated in the Flow Chart.
	Has been changed to:
	A physical examination will be performed by the
	Investigator or designated site-personnel at the
	time point indicated in the Flow Chart.
Rationale for change	Correction of typo
	T-11- 5 2 5- 1 C-5-4-1-1
Section to be changed	Table 5.3.5: 1 Safety laboratory tests
Description of change	baso-phils
	TT114
	Has been changed to:
	basophils
Rationale for change	Correction of typo
Nationale for change	Correction of typo
Section to be changed	5.3.7 Adverse event collection and reporting
Description of change	From signing the informed consent onwards
2 confidence of change	through the Residual Effect period (REP), all
	anough the Residual Effect period (REI), all

c03317678-02 Trial Protocol Page 67 of 69

	AEs (serious and non-serious), and AESIs.
	Has been changed to:
	From signing the informed consent onwards
	through the Residual Effect period (REP), all
	AEs (serious and non-serious), and AESIs must
	be reported.
Rationale for change	Correction of typo
Sadan ta ba aban and	6.2.2 Treatment region
Section to be changed	6.2.2 Treatment period The 3 rd bullet point under "The patient should be
Description of change	instructed" was changed from
	to refrein from voing regave medication before
	to refrain from using rescue medication before Visit 3 if possible. If this turns out not to be
	possible, another supply of rescue medication
	might be dispensed at visit 3
	gan or and paragraphs
	to
	to refrain from using rescue medication before
	Visit 3 if possible. If this turns out not to be
	possible, another supply of rescue medication
	might be dispensed at visit 5
Rationale for change	Correction of typo
Section to be changed	6.2.2 Treatment period
Description of change	The 7 th bullet point under "The patient should be instructed" was splitted from
	to notice the in notice t'a diamage visall or
	to return their patient's diary as well as all unused trial and rescue medication and
	packaging at Visit 6
	puckaging at visit o
	to
	• to return their patient's diary at visit 2,
	visit 3, visit 4, visit 5 and visit 6
	• to return all unused trial and rescue
	medication and packaging at Visit 6
Rationale for change	The patients get a new diary at each visit 1-5 and
	are supposed to return that diary at the very next
	visit
	(225 11 12 12 12 12 12 12
Section to be changed	6.2.3 Follow Up Period and Trial Completion

[figure not shown]
BI Trial No.: 1358.1

c03317678-02 Trial Protocol Page 68 of 69

Description of change	All study procedures according to the Flow Chart
Description of change	All study procedures according to the Flow Chart should be performed. Patients who complete the treatment period should be registered as completed in the IRT system.
	Has been changed to:
	All study procedures according to the Flow Chart should be performed.
Rationale for change	The IRT system does not require to register the termination of a patient's trial participation
Section to be changed	6.2.3 Follow Up Period and Trial Completion
Description of change	Patient who want to discontinue the trial treatment prematurely should be asked to have Visit 6 in the morning after the last application of the trial medication and to have a Visit 7T at least 48 hours after that last application.
	Patients who want to discontinue the trial treatment prematurely should be asked to have Visit 6 in the morning after the last application of the trial medication and to have a Visit 7T at least 48 hours after that last application.
Rationale for change	Correction of typo
Section to be changed	endpoint
Section to be changed	
Description of change	

c03317678-02 Trial Protocol Page 69 of 69

					0
Proprietary confidential information ©	2016 Roehringer Inge	lheim Internation	nal GmbH or one o	r more of its affilia	ated companies
Troprictary confidential information @	zoro Boeminger inge	miemi miternatioi	iai Ginori oi one o	i more or its arring	ated companies
	-				
Rationale for change					

APPROVAL / SIGNATURE PAGE

Document Number: c03317678 Technical Version Number: 2.0

Document Name: clinical-trial-protocol-version-2

2. LIST OF ABBREVIATIONS

Term	Definition / description
AE	Adverse Event
AESI	Adverse Events of Special Interest
ANCOVA	Analysis of Covariance
ASS	Acetyl salicylic acid
AUC	Area Under the Curve
BI	Boehringer Ingelheim
BMI	Body Mass Index
BRPM	Blinded Review Planning Meeting
CI	Confidence Interval
cm	Centimetre
CRA	Clinical Research Assistant/Associate
СТР	Clinical Trial Protocol
CTR	Clinical Trial Report
DBLM	Database Lock Meeting
DBP	Diastolic Blood Pressure
eCRF	Electronic Case Report Form
ЕоТ	End of Text
FAS	Full Analysis Set
g	Gram
GCP	Good Clinical Practice
ICH	International Conference on Harmonisation
IDEA	International Document Management and Electronic Archiving System
IMP	Investigational Medicinal Product
IPV	Important Protocol Violation
kg	Kilogram
MedDRA	Medical Dictionary for Regulatory Activities

Term	Definition / description
MMRM	Mixed Model Repeated Measures
MQRM	Medical Quality Review Meeting
Ν	Newtons
NSAID	Non-steroidal Anti-Inflammatory Drug
PA	Pressure Algometry
POM	Pain on movement
POM _{WP}	Pain on movement of worst procedure
POM _{WP} AUC ₇₂	Area Under the Curve of POM_{WP} assessed until Day 4 morning
POM _{WP} AUC ₁₂₀	Area Under the Curve of POM_{WP} assessed until Day 6 morning
PR	Pulse Rate
РТ	Preferred Term
PV	Protocol Violation
Q1	Lower Quartile
Q3	Upper Quartile
REML	Restricted Maximum Likelihood
REP	Residual Effect Period
SAE	Serious Adverse Event
SAS	Statistical Analysis System
SBP	Systolic Blood Pressure
SD	Standard Deviation
PDL	Patient Data Listing
SOC	System Organ Class
TMM	Trial Member Medicine
TS	Treated Set
TSAP	Trial Statistical Analysis Plan
VAS	Visual Analog Scale
WHO-DD	World Health Organization-Drug Dictionary

3. INTRODUCTION

As per ICH E9 [1], the purpose of this document is to provide a more technical and detailed elaboration of the principal features of the analysis described in the protocol, and to include detailed procedures for executing the statistical analysis of the primary and secondary variables and other data.

This trial statistical analysis plan (TSAP) assumes familiarity with the Clinical Trial Protocol (CTP), including Protocol Amendments. In particular, the TSAP is based on the planned analysis specification as written in CTP Section 7 "Statistical Methods and Determination of Sample Size". Therefore, TSAP readers may consult the CTP for more background information on the study, e.g., on study objectives, study design and population, treatments, definition of measurements and variables, planning of sample size, randomisation.

SAS[®] Version 9.4, or a later version, will be used for all analyses.

4. CHANGES IN THE PLANNED ANALYSIS OF THE STUDY

The following changes to CTP v1 were made and approved in CTP v2, dated 21-Jun-2016

Global Amendment 1:

1. The two endpoints, number of patients with a decrease in POM_{WP} from baseline of at least 30% and 50% respectively were planned to be analysed at the timepoint, before drug application in the morning of day 2 (Visit 2), however no such analysis will be performed as there is no POM assessment scheduled at this timepoint.

In addition, the following changes are made in the TSAP

• Contrary to the protocol, all analyses pertaining to change from baseline were programmed as

Change in endpoint = Endpoint at time x – endpoint at baseline

rather than

Change in endpoint = Endpoint at baseline - Endpoint at time x

To minimize the risk of error by re-programming it was decided not to reverse the calculation. Additionally it was felt that, for the POM assessments in particular, it would be intuitively preferable to show any decrease from baseline as a negative value thus providing an indication of treatment effect.

- - The initial TSAP stated the planned treatment application date/time for Day 6 was to be included in the calculation of the time intervals used in the derivation of the key secondary endpoint, POM_{WP}AUC₁₂₀. However as there is no treatment application scheduled at Day 6, the POM assessment time for Day 6 will be imputed as the actual treatment application date/time for Day 5 evening + 12 hours or alternatively, Day 5 morning + 24 hours if the former is missing.

- Some sites in Germany, during the conduct of the trial, did not have sufficient POM booklets in stock which led to photocopies of the VAS scale being used in the POM assessments. Unfortunately some of these copied VAS scales were not exactly 10cm in length. Similarly for Russian sites, the VAS scale displayed in the POM booklets, printed in Russia, were not always exactly 10cm. As a consequence,
 - all POM measurements will be normalised, prior to analysis, to a 10cm scale.

Boehringer Ingelheim TSAP for BI Trial No: 1358.1

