- B M = Morning; E = Evening; Morning visits should generally be performed between 7:00 am and 11:00 am.
- C Visits 2 and 3 need to be planned so that the evening application of the trial medication can be administered 12 hours (±4 hours) after the morning application.
- Date of Visit 6 has to be agreed based on patient's availability and severity of pain. Standard treatment duration is 5 days (Day 1-5) with Visit 6 on Day 6. Treatment could be shortened to 4 days (with Visit 6 on Day 5) or extended to 6 days (with Visit 6 on Day 7; home procedures indicated in the Flow Chart for Day 5 to be repeated on Day 6) or 7 days (with Visit 6 on Day 8; home procedures indicated in the Flow Chart for Day 5 to be repeated on Day 6 and 7). Visit 7T should be performed at least 2 days and no later than 4 days after Visit 6.
- E For women of childbearing potential only

c03317678-02 Trial Protocol Page 7 of 69

Proprietary confidential information © 2016 Boehringer Ingelheim International GmbH or one or more of its affiliated companies

- G Parameters to be assessed by the patient 0.5 (±5 min), 1 (±10 min but before POM assessments), 3 (±15 min) and 6 (±15 min) hours after the morning application of the trial drug. Results will be entered into the patient diary.
- H Pre = before application; Apl = Application; Post = after application. The application time at each visit is to be documented in the eCRF.
- I Assessment 1 hour (± 10 min) after application of trial medication
- J Optional second dispense of rescue medication
- K Hm = Home procedure; Fllw up = Follow up
- L All five POM assessments need to be performed at Visit 1 before application. Once POM_{WP} is determined, only POM_{WP} and the other POM procedures related to the same stratum (either back or neck pain) as POM_{WP} need to be performed at subsequent assessments (see Section 5.2.1)
- M To be assessed by the patient at home directly before and 1 hour (±10 min) after the morning application of the trial drug
- N To be assessed 1 hour (±10 min) after application of the trial drug and before POM assessments

BI Trial No.: 1358.1

c03317678-02 Trial Protocol Page 8 of 69

Proprietary confidential information © 2016 Boehringer Ingelheim International GmbH or one or more of its affiliated companies

TABLE OF CONTENTS

TITLE I	PAGE	1
CLINIC	AL TRIAL PROTOCOL SYNOPSIS	2
FLOW (CHART	5
TABLE	OF CONTENTS	8
ABBRE	VIATIONS	11
1.	INTRODUCTION	13
1.1	MEDICAL BACKGROUND	13
1.2	DRUG PROFILE	14

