5.2 SECONDARY ENDPOINTS

5.2.1 Key secondary endpoints

• POM_{WP}AUC₇₂ and POM_{WP}AUC₁₂₀

AUC will be calculated as area under the curve from zero to approximately 72 hours (corresponding to $POM_{WP, day 4 \text{ morning post application}}$) or to approximately 120 hours (corresponding to $POM_{WP, day 6 \text{ morning}}$) using the trapezoidal rule divided by the observation time.

$$POM_{WP}AUC_{72} = \frac{1}{t_6} \sum_{i=1}^{6} \frac{1}{2} (POM_{WP}(t_{i-1}) + POM_{WP}(t_i)) * (t_i - t_{i-1})$$

$$POM_{WP}AUC_{120} = \frac{1}{t_7} \sum_{i=1}^{7} \frac{1}{2} (POM_{WP}(t_{i-1}) + POM_{WP}(t_i)) * (t_i - t_{i-1})$$

Study drug application date/times will be the basis for the calculation of respective time intervals.

 $t_0 = 0$,

for i=1 to 6,

 $t_i = ([actual date of application of POM_{WP} assessment i+1] - [actual date of first application (visit 1)]) * 24 + [actual time of application of POM_{WP} assessment i+1] - [actual time of first application (visit 1)] + 1_{post-value}.$

 $t_7 = ([actual date of application on Day 5 evening] - [actual date of first application (visit 1)]) * 24 + [actual time of application on Day 5 evening - actual time of first application (visit 1)] + 12.$

where

$$1_{post-value} = \begin{cases} 0, if \ pre-application \ POM_{WP} \ value \\ 1, if \ post-application \ POM_{WP} \ value \end{cases}$$

Planned assessment times are:

Assessment	t _i
1 (Baseline)	$t_0 = 0$
2 (Day 1 morning, 1 hour after application)	t ₁ = 1
3 (Day 2, morning, 1 hour after application)	$t_2 = 25$
4 (Day 2 evening, before application)	$t_3 = 36$
5 (Day 2 evening, 1 hour after application)	$t_4 = 37$
6 (Day 3, morning, 1 hour after application)	$t_5 = 49$
7 (Day 4, morning, 1 hour after application)	$t_6 = 73$
8 (Day 6, morning)	$t_7 = 120$

For AUC calculation, one or more missing assessments in between POM assessments will be imputed using the planned assessment time and a linear interpolation of the last available assessment before (including baseline, if applicable) and the first available assessment after the missing assessment. If there is no evaluable assessment after the planned time of the missing assessment, planned assessment time and LOCF will be used to impute the value.

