6.7 BASELINE, TIME WINDOWS AND CALCULATED VISITS

Definition of baseline

Baseline values are defined as the last morning assessment prior to randomization and the first drug application on day 1 (Visit 1).

Time windows

Time windows for visits are shown in the Flow Chart in the CTP. Visits 1-5 must be carried out on the specified days, for Visit 6 there is a time window of -1/+2 days, for Visit 7T there is a time window of +4 days.

Calculated visits

Visits which occur outside of the defined visit window are flagged as PVs.

If a single scheduled visit is completed outside of the visit window, as defined in the CTP, that visit will be assigned to the scheduled visit. For example, if a patient completes a visit in the afternoon of day 3, the visit would be assigned to visit number 4.

If two consecutive scheduled visits are missed, but a single visit completed between the visit for both scheduled (but missed) visits, the completed visit will be assigned to the closest scheduled visit. However, the final assignment of the visit should be agreed at a medical quality review meeting (MQRM) or BRPM.

Unscheduled visits are not expected for this study. However, should unscheduled visits occur between non-missed scheduled visits, they are assigned separate visit numbers according to BI convention, but will not be included in the summary statistics and will not be used in any inferential analysis.

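### For the key secondary endpoint AUC120, the SAP times the Visit 6 score only from Day 5 applications, although Visit 6 may fall on Days 5 to 8

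*SAP*

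**What the plan says.** Protocol 5.1.2 defines AUC120 as the trapezoidal area from zero to 120 hours divided by the observation time, with intervals based on application times. Protocol 7.2 places it in the confirmatory hierarchy, after AUC72.

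The timing rule in SAP section 4 is that "the POM assessment time for Day 6 will be imputed as the actual treatment application date/time for Day 5 evening + 12 hours". When the evening time is missing, the fallback is Day 5 morning plus 24 hours. The reason given for imputing a time at all is "as there is no treatment application scheduled at Day 6". The t7 formula in SAP 5.2.1 uses the "actual date of application on Day 5 evening" and does not repeat the morning fallback. For a missing assessment with no later one available, SAP 5.2.1 says that "planned assessment time and LOCF will be used to impute the value".

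Visit 6 is not fixed to Day 6. Footnote D of the protocol Flow Chart says: "Treatment could be shortened to 4 days (with Visit 6 on Day 5". It also allows Visit 6 on Day 7 or 8, with "home procedures indicated in the Flow Chart for Day 5 to be repeated on Day 6" (and on Day 7 for the longest course). Protocol 3.1 ties the choice to severity and availability. Protocol 6.2.3 asks patients who stop early to have Visit 6 the morning after their last application. SAP 6.7 states that "for Visit 6 there is a time window of -1/+2 days", and for a visit outside its window that "that visit will be assigned to the scheduled visit".

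**The concern.** The timing rule covers one of four permitted treatment lengths. For the others, a planned course under the protocol meets either no rule or a rule that gives a time one or two days before the score was taken.

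This matters because t7 enters AUC120 twice: it sets the width of the last trapezoid, about 47 of 120 hours, and it is the divisor. The endpoint is confirmatory, so its value should not depend on a choice left to the programmer. Visit 6 timing may also depend on severity, which can respond to treatment, so equal shares of off-Day-6 visits across arms cannot be taken for granted.

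**Working it through.** **1. The standard case.** Put the first application at 0 h with 12 h between applications. Day 5 evening is 4 × 24 + 12 = 108 h, and 108 + 12 = 120 h. The fallback gives 96 + 24 = 120 h. Both match the planned t7 of 120 h in SAP 5.2.1, so the rule is right for a Day 6 visit.

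**2. The other permitted cases.** Protocol 4.1.4 puts the last application on the evening before Visit 6.

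| Visit 6 | Last application + 12 h | t7 by the SAP rule |
|---|---|---|
| Day 5 | 72 + 12 + 12 = 96 h | none: no Day 5 application |
| Day 6 | 120 h | 120 h |
| Day 7 | 120 + 12 + 12 = 144 h | 120 h |
| Day 8 | 144 + 12 + 12 = 168 h | 120 h |
| Day 3, after a stop on Day 2 evening | 24 + 12 + 12 = 48 h | none |

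In the first and last rows a score exists and SAP 6.7 keeps it as Visit 6. The carry-forward rule does not help, because it covers missing assessments, not an observed score without a time. In the Day 7 and 8 rows, footnote D schedules applications on Day 6, so the reason given in SAP section 4 does not hold for those courses.

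**3. Size of the misdating.** The documents give no pain curve. I assume POM_WP(t) = 70 × 2^(-t/h) mm and vary h from 40 to 120 h. The assessment times are those planned in SAP 5.2.1: 0, 1, 25, 36, 37, 49, 73 and 120 h.

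For h = 60, the trapezoids from 0 to 73 h sum to about 3,468 mm·h. With 30.12 mm at 73 h and 17.50 mm at 120 h, the last piece is (30.12 + 17.50)/2 × 47 = 1,119 mm·h. The reference is (3,468 + 1,119)/120 = 38.23 mm.

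If a score from time T is placed at 120 h, only the last trapezoid changes:

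error = [POM(T) - POM(120)] × 47 / (2 × 120)

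- Day 5, h = 60: (23.09 - 17.50) × 47/240 = +1.09 mm
- Day 7, h = 60: (13.26 - 17.50) × 47/240 = -0.83 mm
- Day 8, h = 60: (10.05 - 17.50) × 47/240 = -1.46 mm

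| h (hours) | Day 5 score at 120 h | Day 7 score at 120 h | Day 8 score at 120 h |
|---|---|---|---|
| 40 | +0.88 | -0.58 | -0.97 |
| 60 | +1.09 | -0.83 | -1.46 |
| 80 | +1.12 | -0.91 | -1.65 |
| 120 | +1.02 | -0.89 | -1.66 |

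The Day 5 column is one possible workaround, not something the SAP prescribes. If the Day 5 score were instead discarded and the Day 4 score carried to 120 h, the error at h = 60 would be +2.47 mm.

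**4. The same cases with the proposed rule, h = 60.**

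- Day 7: interpolated value at 120 h is 30.12 + (13.26 - 30.12) × 47/71 = 18.96 mm; error (18.96 - 17.50) × 47/240 = +0.29 mm.
- Day 8: 30.12 + (10.05 - 30.12) × 47/95 = 20.19 mm; error +0.53 mm.
- Day 5, score carried from 96 to 120 h: last piece (30.12 + 23.09)/2 × 23 + 23.09 × 24 = 1,166 mm·h; error (1,166 - 1,119)/120 = +0.39 mm.

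**5. Between arms.** The shift is the gap in shares times the error per patient. An assumed gap of 10 to 30 percentage points in Day 8 visits gives 0.10 × 1.46 = 0.15 mm to 0.30 × 1.46 = 0.44 mm. The documents give no figure for this gap.

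**The case against.** Dating every in-window Visit 6 near 120 h could be a nominal-visit convention. SAP 5.2.1 speaks of approximately 120 hours, and the Day 6 change analysis also treats any Visit 6 as the Day 6 time point. That is a fair defence for Days 7 and 8, but the SAP does not state the convention, and it leaves t7 undefined for Day 5 visits and earlier stops.

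One could also take *Day 5* to mean the last treatment day. Footnote D repeats the Day 5 procedures on later days, and protocol 6.2.2 expressly asks for the diary time of the last application. Every patient with Visit 6 the morning after the last application would then get a time. This is not the literal wording, and the SAP does not adopt it.

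A reader might infer errors of several millimetres. At h = 60, ending the window at the actual visit gives +4.3, -3.4 and -6.2 mm for Days 5, 7 and 8 against a fixed 0 to 120 h average. These figures combine the non-literal reading with a fixed-window yardstick. Both documents divide by the observation time, so they do not show harm from the rule as written.

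A reader might also infer that all early stops lack a time. A stop after a Day 5 morning application gets one from SAP section 4. For earlier stops, carry-forward dominates: with Visit 6 at 48 h and h = 60, the error is +9.1 mm with the score placed at 120 h and +7.5 mm with the proposed rule, so timing accounts for 1.6 mm.

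Finally, an emptied part of SAP section 4 and the SAS code are not shown, so a handling rule there cannot be excluded. The visible t7 formula is complete and has no branch for these cases.

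**Conclusion.** The gap is real and limited. As written, t7 cannot be computed when Visit 6 is on Day 5 or follows a stop before any Day 5 application, and a Day 7 or 8 score is dated about 24 or 48 h too early. The supported size is about 1 to 1.5 mm per affected patient, with the ranges in the table, on an assumed exponential recovery from 70 mm and against a 0 to 120 h average. Only patients whose Visit 6 is off Day 6 are affected, and their share is not given.

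The documents do not support a claim that the AUC120 comparison is materially biased: the trial is double-blind, visit timing also depends on availability, and the between-arm effect is probably small. Nor is the primary endpoint affected, since its model stops at Day 2 evening. The Day 6 change does not use t7 either. AUC72 could use it only where a missing Day 4 score is interpolated to Visit 6 (about 0.4 mm for Day 7 and 0.7 mm for Day 8, at h = 60). Severity is minor to should-fix: a confirmatory endpoint should not be left to a programming choice that is cheap to settle.

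**What to change.** In both SAP section 4 and SAP 5.2.1, define t7 from the last application before Visit 6: plus 12 h if it was an evening application, plus 24 h if a morning one. This follows protocol 5.1.2, which bases intervals on application times.

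State how the window is handled when t7 is not about 120 h. To match the zero-to-120-hour definition in protocol 5.1.2, interpolate to 120 h when Visit 6 is later, and carry the score forward from its true time when it is earlier, including visits after an early stop. If the sponsor prefers a nominal-visit convention or a window ending at the patient's own visit, the SAP should say so and cover Day 5 visits and early stops.

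Limit the statement that no application is scheduled at Day 6 to the standard 5-day course.

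The cost is SAP wording and a small programming change. The last application time is already collected, so no new data are needed.
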